#### **4.5.2 Laboratory assessments**

Summary of both hematology and chemistry laboratory values categorized based on common toxicity criteria grade will be presented by treatment groups. All laboratory data will be listed and values that are out of normal range will be indicated (*Table 21*).

#### **4.5.3 Vital signs**

Observed vital sign values and changes from baseline to visits will be summarized by treatment groups. All vital signs data will be listed. The analysis of vital signs will focus on the incidence of clinically relevant abnormalities. The number of subjects evaluated and the number and percentage of subjects with clinically relevant post-baseline abnormalities at each visit will be presented (*Table 22*).

### **5. Appendices**

#### **5.1 Statistical Analysis Plan Table shells**

Table 1. Demographic Characteristics

	All	Viaskin® milk	Placebo	
Age, year				
n				
n missing				
Mean ± SD				
Median (IQR)				
Range				
4-11 years old, n (%)				
12-17 years old, n (%)				
Gender, n (%)				
Male				
Female				
Ethnicity, n (%)				
Hispanic or Latino				
Neither Hispanic nor Latino				
Race, n (%)				
American Indian or Alaska Native				
Asian				
Native Hawaiian or other Pacific Islander				
Black or African American				
White				
Does not know				
Refuse				

Values will be expressed as frequency counts (percentages) unless indicated.

SD, Standard deviation; IQR, Interquartile range

**Table 1 specification** Repeat with ITT population and per protocol (PP) population separately as Table 1A and Table 1B, respectively.

Table 2. Medical History by System Organ Class and Preferred Term

	All	Viaskin® milk	Placebo	
Constitutional				
Ears, Nose, Mouth, Throat				
Cardiovascular				
Respiratory				
Gastrointestinal				
Genitourinary				
Integumentary				
Musculoskeletal				
Neurological				
Hematologic				
Lymphatic				
Allergic				
Immunologic				
Endocrine				
Asthma				
Allergic Rhinitis				
Food Allergy				
Atopic Dermatitis				
Other				

Values will be expressed as frequency counts (percentages) [n (%)].

**Table 2 specification**

Repeat with ITT population and PP population separately as Table 2A and Table 2B, respectively.

Table 3. Summary Statistics for Vital Signs

	All	Viaskin® milk	Placebo	
Height, cm				
Baseline #				
Visit 10 #				
Visit 16 #				
Weight, kg				
Baseline				
Visit 10				
Visit 16				
Blood pressure, mmHg				
Baseline				
Visit 10				
Visit 16				
Pulse rate, beats/min				
Baseline				
Visit 10				
Visit 16				
Respiratory rate, breaths/min				
Baseline				
Visit 10				
Visit 16				
Temperature, °C				
Baseline				
Visit 10				
Visit 16				

# Baseline, Visit 10, and Visit 16 correspond to day 1, end of the double-blind treatment and end of the open-label treatment, respectively.

Values will be expressed as n, n missing, mean  $\pm$  SD, median (IQR), and range.

Table 4A. Summary Statistics for Laboratory Results (Hematology)

	All	Viaskin® milk	Placebo	
RBC count, MIL/ $\mu$ L				
Baseline #				
Visit 10 #				
Visit 16 #				
WBC count, Thou/ $\mu$ L				
Baseline				
Visit 10				
Visit 16				
Hemoglobin, g/dL				
Baseline				
Visit 10				
Visit 16				
Hematocrit, %				
Baseline				
Visit 10				
Visit 16				
Platelet count, Thou/ $\mu$ L				
Baseline				
Visit 10				
Visit 16				
Segmented neutrophils, cells/ $\mu$ L				
Baseline				
Visit 10				
Visit 16				
Lymphocytes, cells/ $\mu$ L				
Baseline				
Visit 10				
Visit 16				
Monocytes, cells/ $\mu$ L				
Baseline				
Visit 10				
Visit 16				

Eosinophils, cells/ $\mu$ L				
Baseline				
Visit 10				
Visit 16				
Basophils, cells/ $\mu$ L				
Baseline				
Visit 10				
Visit 16				

# Baseline, Visit 10, and Visit 16 correspond to day 1, end of the double-blind treatment and end of the open-label treatment, respectively.

Values will be expressed as n, n missing, mean  $\pm$  SD, median (IQR), and range.

Table 4B. Summary Statistics for Laboratory Results (Chemistry)

	All	Viaskin® milk	Placebo	
Total protein, g/dL				
Baseline #				
Visit 10 #				
Visit 16 #				
Blood urea nitrogen, mg/dL				
Baseline				
Visit 10				
Visit 16				
Creatinine, mg/dL				
Baseline				
Visit 10				
Visit 16				
ALP (Alkaline phosphatase), U/L				
Baseline				
Visit 10				
Visit 16				
ALT (Alanine aminotransferase), U/L				
Baseline				
Visit 10				
Visit 16				
AST (aspartate aminotransferase), U/L				
Baseline				
Visit 10				
Visit 16				
Total bilirubin, mg/dL				
Baseline				
Visit 10				
Visit 16				

---

# Baseline, Visit 10, and Visit 16 correspond to day 1, end of the double-blind treatment, and end of the open-label treatment, respectively.

Values will be expressed as n, n missing, mean  $\pm$  SD, median (IQR), and range.

---

**Table 4 (4A and 4B) Specification**

Laboratory results (Hematology and Chemistry) will also be summarized in the “Other” unit(s) if there is/are “Other” unit(s).

Table 5. Subject Disposition

	All	Viaskin® milk	Placebo
Randomized, n (%)			
Yes			
No			
Study population, n (%)			
Safety			
Intent-to-treat			
Per protocol			
Received study medication, n (%)			
Yes			
No			
Completed double-blind period, n (%)			
Yes			
No			
Discontinued double-blind period, n (%)			
Yes			
No			
Completed open-label period, n (%)			
Yes			
No			
Discontinued open-label period, n (%)			
Yes			
No			

Values will be expressed as frequency counts (percentages).

Table 6. Descriptive Statistics for Maximum Esophageal Eosinophil Count (Primary Efficacy Endpoint)

	Viaskin® milk (n=xx)			Placebo (n=xx)		
	Baseline	Visit 10	Change	Baseline	Visit 10	Change
4-11 years old						
n						
n missing						
Mean $\pm$ SD						
Median (IQR)						
Range						
12-17 years old						
n						
n missing						
Mean $\pm$ SD						
Median (IQR)						
Range						
4-17 years old (All)						
n						
n missing						
Mean $\pm$ SD						
Median (IQR)						
Range						

SD, Standard deviation.

Visit 10 is the end of treatment. Change = Visit 10 – Baseline.

### Table 6 specification

Repeat with ITT population and PP population separately as Table 6A and Table 6B, respectively.

Table 7. Maximum Esophageal Eosinophil Count Analysis at the End of Double-blind Treatment (Primary Efficacy Analysis, ANCOVA models)

	Least square means	95% CI
Viaskin® milk	xx.xx	-
Placebo	xx.xx	-
Difference (Viaskin® milk – Placebo)	xx.xx	(xx.xx, xx.xx)

Number of observations used: xxx

Least square means from the analysis of covariance (ANCOVA) model including treatment group and baseline maximum esophageal eosinophil count as covariates will be reported. A two-sided 95% confidence interval (CI) for the difference in least square means between two treatment groups will be reported.

**Table 7 specification**

Repeat with ITT population and PP population with LOCF separately as Table 7A and 7B, respectively.

Table 8. Summary Statistics for Total Esophageal Endoscopy Score (Secondary Efficacy Endpoint)

	All	Viaskin® milk	Placebo	Median Difference (95% CI) #
Total esophageal endoscopy score				
Baseline				
Visit 10				
Visit 16				
Change from baseline to visit 10				xx (xx, xx)
Change from baseline to visit 16				xx (xx, xx)

Values will be expressed as n, n missing, mean  $\pm$  SD, median (IQR) range.  
# Hodges-Lehmann estimate with 95% CI for median differences between two treatment groups will be reported.

**Table 8 specification**

Repeat with ITT population and PP population separately as Table 8A and Table 8B, respectively.

Table 9A. Total Esophageal Endoscopy Score Analysis at the End of the Double-blind Treatment (Secondary Efficacy Analysis, ANCOVA Models)

	Least square means	95% CI
Viaskin® milk	xx.xx	-
Placebo	xx.xx	-
Difference (Viaskin® milk – Placebo)	xx.xx	(xxxx,xx.xx)

Number of observations used: xxx.

Least square means from the analysis of covariance (ANCOVA) model including treatment group and total esophageal endoscopy score at baseline as covariates will be reported. A two-sided 95% confidence interval (CI) for the difference in least square means between two treatment groups will be reported.

Table 9B. Total Esophageal Endoscopy Score Analysis at the End of the Open-label Treatment (Secondary Efficacy Analysis, ANCOVA Models)

	Least square means	95% CI
Viaskin® milk	xx.xx	-
Placebo	xx.xx	-
Difference (Viaskin® milk – Placebo)	xx.xx	(xx.xx, xx.xx)

Number of observations used: xxx.

Least square means from the analysis of covariance (ANCOVA) model including treatment group and total esophageal endoscopy score at baseline) as covariates will be reported. A two-sided confidence interval (CI) for the difference in least square means between two treatment groups will be reported.

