The time of application and removal of each Viaskin® will be noted on the subject diary cards (see Section 10.10), along with any observed AE(s) (local and/or distant). Application of the Viaskin® at a similar time for each application (am or pm) is recommended.

After Visit 10, all subjects will continue treatment with open-label Viaskin® Milk 500 µg for up to 11 additional months. It is permitted at the discretion of the Investigator, to postpone the application of the first patch up to a maximum of 7 days after V10.

To increase the safety of subjects at the beginning of the open-label treatment period, in particular for subjects crossing over from placebo to the active Viaskin Milk treatment, the daily duration of application will again be adapted from Visit 10 for the first weeks of treatment: 6 hours/day during the first week, 12 hours/day during the second week, and for an entire 24 hours daily from the third week onwards. During the period of 24 hours of daily application, flexibility of 24 hours ± 4 hours of daily application is permitted.

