### **2.2.3 Secondary efficacy objectives**

The secondary efficacy objectives are:

- a.** To describe the EoE symptoms score and global assessment score at end of each treatment period at 11 months (end of the double-blind treatment) and 22 months (end of the open-label treatment) in each treatment group and to determine if there

is a difference in improvement of the EoE symptom score between the active treatment group and the placebo group.

- b. To assess if there is a difference in the mean esophageal eosinophil count between the active treatment group and the placebo group at end of each treatment period at 11 and 22 months.
- c. To assess if the changes in mean and maximum esophageal eosinophil count from baseline to end of each treatment period at 11 and 22 months are different between the active treatment group and the placebo group.
- d. To assess if the percentages of subjects with  $\leq 1$  eosinophils/HPF (excellent response), subjects with 2-14 eosinophils/HPF (good response), and subjects with  $\geq 15$  eosinophils/HPF (poor response) at the end of each treatment period at 11 and 22 months are similar between the active treatment group and the placebo group.
- e. To assess if there is a difference in esophageal endoscopy score at the end of each treatment period at 11 and 22 months and to examine the changes in esophageal endoscopy score from baseline to the end of each treatment period at 11 and 22 months between the active treatment group and the placebo group.
- f. To examine the changes in the eosinophilic esophagitis quality of life score from baseline to the end of each treatment period at 11 and 22 months between the active treatment group and the placebo group.
- g. To examine the changes in the composite score, which will be calculated using four measures (Eosinophils/HPF, Esophageal Endoscopic Reference Score (EREFS), Pediatric Eosinophilic Esophagitis Symptoms Score (PEESS), and investigator assessment of EoE symptom activity), from baseline to the end of treatment period at 11 and 22 months between the active treatment group and the placebo group  
[Composite score = Maximum Eosinophils per HPF + 10\*EREFS + 2\*PEESS + 5\*  
(Investigator assessment of EoE symptom activity)].

- h. To assess if there is difference in time to development symptoms after milk reintroduction at month 9 and 20 between the active treatment group and the placebo group.

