### **2.3 Treatments**

Subjects will be randomized to receive Viaskin® with milk protein (500 µg of milk proteins) or placebo during the first year in the study. Viaskin® milk contains a dry deposit of natural milk protein formulated without adjuvant. The placebo treatment will consist of a similar formulation, but will be devoid of milk proteins. During the second year in the study (after third upper endoscopy), all subjects will receive open-label Viaskin® (500 µg of milk proteins).

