## 2.5 Study visits

There are at least three visits during the screening period that will occur before enrollment and randomization to the active treatment phase of the SMILEE study. Fully eligible subjects will be required to attend 17 study visits as follows:

**Screening period:** Potentially eligible subjects will be enrolled into the study (Visit 1) to confirm Treatment Period study eligibility and obtain a number of study endpoints. The GI group will follow SOC procedures, but the dates of the first (Visit 2) and second (Visit 3) endoscopies with biopsies will not be mandated by the investigative team, but by the GI group for clinical care. The second upper endoscopy/biopsy will be done at a minimum of 6 weeks after milk-removal, per clinical care. If a patient meets eligibility criteria for the Treatment Period of SMILEE, s/he will be referred to the Allergy/Immunology division for continuation in the study. If the results of the first or second endoscopy with biopsies confirm ineligibility, the subject may be considered as screen failed and may not continue in the study.

Visit 1: Informed Consent obtained: milk introduction.

Visit 2: One week to 2 months after milk-introduction. Subjects have a SOC upper endoscopy/biopsy performed to confirm the diagnosis of EoE. Milk is removed from the diet.

Visit 3: Subjects have a second SOC upper endoscopy/biopsy to confirm milk induced EoE performed after a minimum of 6 weeks under milk-free diet.

If a subject has an endoscopy that confirms milk responsive EoE in the preceding 12 months, they will not need a repeat endoscopy to be eligible for the study.

**Treatment period:** There will be seven visits during the treatment period:

Visit 4 (Day 1): This visit corresponds to the first day of treatment and can be performed as soon as the results of the upper endoscopy and biopsy at Visit 3 are available and there is confirmed eligibility into the study.

Visit 5: This corresponds to day 8 of treatment.

Visit 6: This corresponds to month 1 of treatment.

Visit 7: This corresponds to month 3 of treatment.

Visit 8: This corresponds to month 6 of treatment.

Visit 9: This corresponds to month 9 of treatment (milk-reintroduction).

Visit 10: One week to 2 months after milk reintroduction. During this time, subjects will have weekly calls to monitor symptoms. Subjects have a third SOC upper endoscopy/biopsy. This is the end of double-blind treatment. The open-label treatment period will start on that day.

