##### **4.4.2.1 Total esophageal endoscopy score**

The total score for each subject will be calculated and summary statistics at baseline, end of the double-blind treatment, and end of the open-label treatment as well as the changes from baseline to end of the double-blind treatment and to end of the open-label treatment will be presented by treatment groups (*Table 8*). Hodges-Lehmann estimate with 95% CI for difference of median of the changes in esophageal endoscopy

scores between two treatment groups will be reported. The total score at the end of the double-blind treatment and at the end of the open-label treatment between two treatment groups will be analyzed separately using ANCOVA as described in Section 4.4.1. The least square means for the treatment groups, difference in least square means between the treatment groups, and a two-sided 95% CI for the difference between the treatment groups will be presented (*Table 9*).

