# Hodges-Lehmann estimate with 95% CI for median differences between two treatment groups will be reported.

### Table 12 specifications

Repeat with ITT population and PP population separately as Table 12A and Table 12B, respectively.

Table 13A. Summary Statistics for Response rate at the End of the Double-blind Treatment (Secondary Efficacy Endpoint)

	All	Viaskin® milk	Placebo	Relative Risk (95% CI)
Response rate, n (%)				
Excellent ( $\leq 1$ eosinophils/HPF)				
Good (2-14 eosinophils/HPF)				
Poor ( $\geq 15$ eosinophils/HPF)				
Values will be expressed as frequency counts (percentages).				

Table 13B. Summary Statistics for Response rate at the End of the Open-label Treatment (Secondary Efficacy Endpoint)

	All	Viaskin® milk	Placebo	Relative Risk (95% CI)
Response rate, n (%)				
Excellent ( $\leq 1$ eosinophils/HPF)				
Good (2-14 eosinophils/HPF)				
Poor ( $\geq 15$ eosinophils/HPF)				
Values will be expressed as frequency counts (percentages).				

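### The SAP presents the 22-month (Visit 16) comparison as active versus placebo, although every continuing subject has been on active patches since Visit 10

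*SAP*

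**What the plan says.** **Treatment after Visit 10.** SAP 2.3 states: "During the second year in the study (after third upper endoscopy), all subjects will receive open-label" Viaskin. SAP 2.5 says of Visit 10: "This is the end of double-blind treatment. The open-label treatment period will start on that day". Protocol 8.5.1 agrees: "all subjects will continue treatment with open-label Viaskin® Milk 500 µg for up to 11 additional months".

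**Objectives.** SAP 2.2.3(b) asks about a difference in mean eosinophil count "between the active treatment group and the placebo group at end of each treatment period at 11 and 22 months". Objectives c to g have the same form. Objective a asks whether symptom improvement differs between the arms, and h compares time to symptoms after the month 9 and month 20 milk reintroductions.

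**Analyses.** SAP 4.4.2.1 says that the endoscopy score "at the end of the open-label treatment between two treatment groups will be analyzed separately using ANCOVA". Table 9B, "Total Esophageal Endoscopy Score Analysis at the End of the Open-label Treatment", carries a row for Viaskin minus placebo with a 95% CI. Its rows are the same as those of Table 9A, which covers the double-blind period. Table 13B, "Response rate at the End of the Open-label Treatment", has a relative-risk column. Tables 8, 12, 14 and 15 have median-difference columns that extend to Visit 16, and the Table 11 footnotes promise a median difference and a relative risk.

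**Arm labels and missing data.** SAP 4.1 keeps ITT subjects in their randomized arm, so those who cross over stay under the placebo heading. SAP 3.3 imputes missing secondary values by last observation carried forward (LOCF).

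**Purpose of the extension.** Protocol 8.1 gives it as long-term safety and efficacy of active treatment for up to 22 months. Neither document describes Visit 16 as an early-versus-delayed-start comparison or says how a null difference should be read.

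**The concern.** At Visit 10 the arms differ in whether they have had active patches. At Visit 16 they differ only in how long. A table that prints the second contrast under the labels of the first invites the reader to take it as a treatment effect. A difference near zero could then be reported as an effect that was absent or lost, when the former placebo subjects may simply have caught up. A non-zero difference would be no easier to interpret, because year-2 diet is set by the subject's own Visit 10 result.

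At stake is what the trial can say at 22 months. The primary endpoint is taken at Visit 10, before any crossover, and is not touched.

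**Working it through.** The documents give no planning figure for a Visit 16 comparison, so there is none to reproduce. The check sets the passages side by side.

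**1. Active exposure by arm.** Protocol 8.1 builds each treatment period as 9 months off milk plus up to 2 months on milk, so up to 11 months.

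| Randomized arm | Active months by Visit 10 | Active months by Visit 16 |
|---|---|---|
| Viaskin Milk | up to 11 | up to 11 + 11 = 22 |
| Placebo | 0 | up to 0 + 11 = 11 |

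**2. What each contrast estimates.** Let E(m) be the mean effect of m months of active patches on any chosen score, with E(0) = 0. Let D be the part of the arm difference that comes from unequal year-2 milk exposure.

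- Visit 10: E(11) − E(0) = E(11). This is efficacy against placebo.
- Visit 16: E(22) − E(11) + D. This is the increment from the earlier start, plus a diet term.

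Protocol 8.1 extrapolates that 9 to 11 months of treatment would be adequate. If the effect is complete by then, E(22) = E(11) and the drug part of the Visit 16 contrast is 0, whatever the size of E(11). If the effect builds more slowly, E(22) − E(11) is not zero, but it is still not E(11).

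**3. The diet term.** Under SAP 2.1, subjects with ≥15 eosinophils/hpf at the third endoscopy go milk-free for 9 months and then reintroduce milk. Those with <15 continue milk for up to 11 months. If the drug works, more of the Viaskin arm falls in the second group and more of the placebo arm in the first. The arms then reach Visit 16 with different milk exposure because of the Visit 10 outcome. The documents do not allow the size of D to be calculated.

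**4. Who is in the placebo column.** A placebo subject who leaves before Visit 10 never receives an active patch. Visit 17, used for early termination, has no scheduled endoscopy, so LOCF would carry a screening endoscopy score into the ITT Visit 16 result.

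**5. Baseline for within-arm change in counts.** SAP 4.4.1 sets baseline at Day 1, but no biopsy is scheduled then. The two screening biopsies are ≥15 on milk and 0–10 off milk by eligibility. Take a Visit 16 mean of 10 purely as an illustration (it is the planning mean for the active arm at Visit 10):

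- milk-free baseline: change from 10 − 10 = 0 to 10 − 0 = +10;
- on-milk baseline: change of 10 − 15 = −5 or more negative.

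The sign depends on which biopsy is used. Change from Visit 10 to Visit 16 avoids this, since both visits are on milk.

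**The case against.** The best defence is that nothing here is invalid in itself. The SAP discloses the open-label switch in 2.1 and 2.3, classifies subjects by randomized arm, and so estimates a legitimate early-versus-delayed-start contrast, the only randomized comparison available at Visit 16. It also tabulates change from baseline to Visit 16 by arm in Tables 8, 10, 11, 12, 14 and 15, and section 4 plans longitudinal models that cover both treatment periods. No passage says that a null would be read as failure.

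Most of this stands. The contrast can be estimated and need not be deleted, and within-arm changes are partly in place. What does not stand is the labelling: the objectives ask about an active group and a placebo group at 22 months, and Table 9B is headed a secondary efficacy analysis.

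A reader might also infer a stronger claim: that the expected difference falls from 50 − 10 = 40 at Visit 10 to 0 at Visit 16, leaving a 5% chance of a positive test with a fully effective drug. The documents do not support attaching those figures:

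- The means of 10 and 50 are planning values for maximum eosinophil count, and the SAP tables for that count (6 and 7) stop at Visit 10.
- Table 9B concerns the endoscopy score, which has no planning mean or SD.
- The SAP plans estimates with 95% CIs at Visit 16, not tests. The protocol synopsis lists between-group tests only in general terms.
- A difference of exactly 0 assumes a complete effect by about 11 months and no diet effect.

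**Conclusion.** The point holds as one of labelling and interpretation. As written, the SAP would present up to 22 against up to 11 months of active treatment as active versus placebo, and that contrast cannot answer objectives b to h, or the between-group part of a, for the open-label period. A small or zero difference is what an effective drug would produce if its effect is largely complete by 9 to 11 months. That condition is the protocol's own extrapolation, not an established fact, and the diet term could move the difference either way. No power or magnitude figure is justified.

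The conclusion covers continuing subjects only, since placebo subjects who leave before Visit 10 are never exposed. It does not show that the between-arm estimate is invalid, and it does not touch the primary analysis.

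**What to change.** Before database lock, amend the SAP as follows.

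- **Objectives.** Restrict the active-versus-placebo wording in 2.2.3(a) to (h) to the double-blind period. Objective h needs this too, because of its month 20 part.
- **Column labels at Visit 16.** Use *Viaskin then Viaskin (up to 22 months active)* and *Placebo then Viaskin (up to 11 months active)*.
- **Main Visit 16 result.** Report within-arm change with 95% CI. Keep the baseline-to-Visit 16 changes already tabulated and add Visit 10 to Visit 16 change, especially for the former placebo arm.
- **Baseline.** For eosinophil counts, state which screening biopsy is baseline.
- **Between-arm estimates.** Where one is kept at Visit 16 (Tables 8, 9B, 11, 12, 13B, 14, 15), label it early versus delayed start, descriptive, and not a treatment effect against placebo. Note that diet in year 2 depended on the Visit 10 result.
- **LOCF.** Do not carry placebo subjects who left before Visit 10 into the placebo-then-Viaskin results.

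The cost is SAP text and table shells, with no new visits, procedures or data. The downside is one fewer estimate presented as a treatment effect. The within-arm changes are uncontrolled and still affected by diet, and should be described that way.
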